3.3. Study participants

Study participants: The study participants will be drawn from households enrolled in the REVIVE sample (Listahanan 3 eligible households) and residing within the selected study clusters. For the household survey, the primary respondent will be the designated meal planner. For the diet assessment component, eligible households must have at least one woman of reproductive age (15–49 years) with (or without) an index youngest child aged 0–59 months.

Inclusion and exclusion criteria: Inclusion criteria include enrollment in the REVIVE sample, residency in the study cluster, and provision of informed consent. Households will be excluded if a member has a severe illness preventing participation or if informed consent cannot be obtained.

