- **Hunger and food insecurity:** Food insecurity and hunger were measured using a structured household questionnaire covering experiences over the previous four weeks, adapted from internationally validated food insecurity experience scales. Respondents were asked whether, due to lack of money or other resources, their household: (i) worried about not having enough food; (ii) was unable to eat healthy and nutritious food; (iii) ate only a limited variety of foods; (iv) skipped meals; (v) ate less than they felt they should; (vi) ran out of food; (vii) went to sleep hungry; or (viii) went a whole day and night without eating. For each occurrence-based question, respondents were further asked about the frequency of the experience during the recall period. These items capture increasing severity of food insecurity, from anxiety about food access to extreme deprivation, and were used to construct categorical indicators of food insecurity severity as well as continuous indices for impact analysis.
- **Nutritional and health outcomes:** For children, we will calculate the height-for-age z-scores (HAZ), weight-for-age z-scores (WAZ) and weight-for-height z-scores (WHZ) using the WHO growth standard. We will use the WHO cut-offs to interpret children's body weight, i.e., underweight, stunting, wasting. For WRA, BMI will be used as one of the markers of nutritional status. BMI will be calculated as $\text{weight}/\text{height}^2$. We will use the WHO cut-offs, i.e., underweight as BMI < 18.5, overweight as BMI 25.0 to 29.9, and obese as BMI ≥ 30.0 . We will also use the cut-offs for Asian populations.

Child health outcomes were assessed using a two-week recall period, during which the primary caregiver reported whether each eligible household member experienced any of the following symptoms: fever, cough/cold, fast or short breathing, diarrhea, fatigue, nausea or vomiting, serious underweight, or a diagnosed micronutrient deficiency (e.g., vitamin A and/or iron deficiency).

- **Household Food and Non-Food Expenditures**

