3.6. Data collection households and individuals

- **Household survey:** household-level data will be collected using a structured and pretested questionnaire which. The household survey will begin with a roster of all household members to establish composition and basic demographic characteristics. The meal planner will subsequently respond to modules related to:
 - Nutrition knowledge
 - Household food consumption patterns over specified recall periods;
 - Food and non-food expenditures;
 - Household experiences related to food access;
 - Participation in social protection and assistance programs;
 - Income sources and other receipts during the reference period;
 - Engagement in gardening, foraging, and entrepreneurial activities.
 - Household assets

Where relevant, recall periods will follow those defined in the outcome descriptions (e.g., seven-day, four-week, six-month, or 12-month reference periods), and enumerators will use standardized probes to improve accuracy and completeness of responses.

- **Individual-Level Data Collection**

For women of reproductive age (WRA) and children under five years, we will conduct dietary intake assessment using 24-hour recall and anthropometric measurements.

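### Fixed adult BMI cut-offs for women aged 15–49 come with no age-specific reference for adolescents and no stated exclusion of pregnant women

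*Protocol*

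**What the plan says.** Section 3.5 of the protocol, under secondary outcomes, names the group and the measure: "For WRA, BMI will be used as one of the markers of nutritional status". It then fixes the categories: "We will use the WHO cut-offs, i.e., underweight as BMI < 18.5, overweight as BMI 25.0 to 29.9, and obese as BMI" of 30.0 or more. A second set follows without values or conditions: "We will also use the cut-offs for Asian populations".

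The age range comes from section 3.3, where households in the diet assessment component need "at least one woman of reproductive age (15–49 years" of age, with or without a child under five. The only exclusions are these: "Households will be excluded if a member has a severe illness preventing participation or if informed consent cannot be obtained". Pregnancy is not among them.

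The section on data collection from households and individuals (the second one numbered 3.6) says that for women of reproductive age and children under five "we will conduct dietary intake assessment using 24-hour recall and anthropometric measurements". It sets no limit by pregnancy or age. For children, section 3.5 does use a growth reference, including "weight-for-height z-scores (WHZ) using the WHO growth standard".

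**The concern.** Two groups within 15–49 years do not fit a fixed adult scale. Adolescents are still growing and normal BMI rises with age, so a constant 18.5 labels some girls underweight who are normal for their age. In pregnancy, measured weight includes the fetus, fluid and gestational gain. A woman can therefore enter the overweight category, or leave the underweight category, without any change in the nutritional status that the outcome is meant to describe.

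The same section recognises both principles elsewhere. It uses WHO growth-standard z-scores for children, and it notes that the GDQS was validated in women who were neither pregnant nor lactating. Neither safeguard is carried over to women's BMI.

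At stake is whether the reported prevalences of underweight and overweight can be interpreted, and how sharply voucher effects on them can be seen.

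**Working it through.** The protocol gives no figure for this outcome, so there is nothing to reproduce. The check has two parts: whether the text closes the gap, and how large the effect could be.

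**Does any section close the gap?**
- Age range: 15–49 years (3.3).
- Group for BMI: women of reproductive age, no subgroup removed (3.5).
- Cut-offs: below 18.5, 25.0–29.9, 30.0 and above, plus Asian values not stated (3.5).
- Exclusions: severe illness or no consent (3.3).
- Listed demographics: age, sex, schooling, employment (3.6, Additional variables). Age is available; pregnancy status is not listed.
- Participants under 18 are foreseen, since parental consent for minors is provided for (Ethical considerations).

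No section supplies an adolescent reference or a pregnancy rule for BMI.

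**Can pregnancy weight cross a cut-off?** BMI = weight / height². Heights and weights here are illustrative.
- 1.50 m, 50 kg: 50 / 2.25 = 22.2. After a gain of 8 kg: 58 / 2.25 = 25.8, counted as overweight.
- Gain needed to reach 25 from starting BMI b at height h: (25 − b) × h². At 1.50 m: 11.25 kg from BMI 20, 6.75 kg from 22, 2.25 kg from 24. Over 1.45–1.55 m and BMI 20–24, the range is 2.1 to 12.0 kg.
- At 1.50 m one BMI unit is 2.25 kg, so a woman one unit below 18.5 leaves underweight after that gain.

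Some pregnant women cross a cut-off and others do not.

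**Effect on prevalence.** Added points = 100 × share of women in the group × share of that group wrongly classified. All shares are assumptions.

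| Group | Share of women | Share wrongly classified | Added points |
|---|---|---|---|
| Pregnant, counted overweight | 3% to 10% | 20% to 40% | 0.03 × 0.20 = 0.6 to 0.10 × 0.40 = 4.0 |
| Aged 15–19, counted underweight | 5% to 15% | 10% to 20% | 0.05 × 0.10 = 0.5 to 0.15 × 0.20 = 3.0 |

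If ages were evenly spread, 15–18 would be 4/35 = 11.4% and 15–19 would be 5/35 = 14.3%. Both lie inside the assumed 5–15%. The underweight range covers the adolescent part only. Pregnancy works against it by lifting some women above 18.5, and that offset is not quantified.

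**Effect on the comparison between arms.** Suppose true overweight is 30% against 35%, with 1258 control and 1364 first-arm households (Table 1) taken as one woman each, two-sided alpha 0.05 and no clustering. If a fraction f of women who are not overweight is counted as overweight in both arms, the observed proportion is p + (1 − p)f and the difference shrinks by the factor (1 − f).

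| f | Observed proportions | Difference | Power |
|---|---|---|---|
| 0 | 30.0% vs 35.0% | 5.0 points | 0.78 |
| 0.02 | 31.4% vs 36.3% | 4.9 points | 0.755 |
| 0.04 | 32.8% vs 37.6% | 4.8 points | 0.73 |

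The direction is unchanged and the loss is modest.

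**The case against.** The strongest reply is that the pregnancy half argues from silence. The protocol never says that pregnant women are classified, the questionnaire is not shown and may ask about pregnancy, and the choice of women entering a derived secondary outcome is often left to the statistical analysis plan. The 15–49 range is a household eligibility rule for the diet component, and other wording suggests that many of the measured women are mothers, so the adolescent share may be small. BMI is secondary and is only one of several possible markers.

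Part of this stands. The pregnancy half does rest on the absence of an exclusion, it cannot be said that pregnancy status goes unrecorded, and the stakes are limited. But the protocol does not leave the classification open: it names the cut-offs and the group. Women without a child are also eligible, so adolescents are not ruled out. And a later analysis plan can exclude pregnant women only if their status was recorded when they were weighed, which the protocol does not secure.

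A reader might also infer three stronger things that the documents do not support.
- **That the endpoint reverses direction in pregnant women.** Leaving underweight through weight gain is the same direction as in other women, and a move towards overweight can follow a voucher in non-pregnant women too.
- **That 16–21% of women are misclassified.** Adding 11.4% (even ages, 15–18) to an assumed 5–10% pregnant gives the share whom the rule may not fit. Only some of them would be classified wrongly, and the sum counts pregnant adolescents twice.
- **That the comparison between arms is biased.** Randomisation should make age mix and pregnancy similar across arms. Bias would need the vouchers to change pregnancy frequency or gestational gain, or a chance imbalance in age.

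**Conclusion.** The point holds as a badly fixed rule for one secondary outcome. Followed literally, it misclassifies some adolescents and some pregnant women. Under the assumed shares, overweight prevalence is overstated by about 0.6–4.0 points and underweight by about 0.5–3.0 points. The documents supply none of these shares, and the number of adolescents below 18.5 who are normal for their age depends on a reference that they do not contain. The adolescent half rests on explicit text, and the pregnancy half on a missing exclusion. The main harm is to the prevalences. Voucher effects are slightly diluted, and their direction is not affected. The change is worth making because it is cheap and because one part of it must be in place before measurement.

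**What to change.** - Record pregnancy status for each woman at the anthropometry visit, and state in section 3.5 that pregnant women are excluded from mean BMI and from all BMI categories.
- For women under 19, use WHO BMI-for-age z-scores.
- Keep the adult WHO and Asian cut-offs for non-pregnant women aged 19–49, and give the Asian values.
- Report adolescents and adults separately.

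The cost is one question, unless the questionnaire already asks it, and a few lines of analysis code. Age is already collected, so the adolescent part needs no new data. The BMI analysis loses the pregnant women, which makes the sample for one secondary outcome slightly smaller. Design, sample size and primary outcomes are untouched.

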3.6. Additional variables

- **Demographic characteristics** (all household members): age, sex, schooling and employment for all household members.
- **Crop Gardening and Foraging:** Households will be asked whether they maintain a personal garden or access a shared or public garden to cultivate or forage vegetables and fruits for household consumption. For households reporting engagement in gardening or foraging activities, respondents will be asked to list the specific crops cultivated or gathered for home use. These data will allow assessment of own-production as a supplementary source of food and its potential contribution to household dietary diversity and food security.
- **Entrepreneurial / Own-Account Activities:** Information on household entrepreneurial or own-account activities will be collected to capture income-generating activities undertaken by the respondent or any household member during the reference period (April 2025 to April 2026). Respondents will be asked about engagement in crop farming, gardening, livestock and poultry raising, fishing, and food-related enterprises.

The survey will also collect information on non-agricultural entrepreneurial or own-account activities undertaken by any household member during the reference period (April 2025 to April 2026). These activities include wholesale and retail trade, manufacturing or processing, transportation and storage services, and other entrepreneurial activities not previously captured.

- **Participation in Other Support Programs**
Information will be collected on household participation in government and private social protection, insurance, and assistance programs. For each listed program, respondents will be asked whether they or any household member have ever been a member or beneficiary and whether they are currently enrolled. If the household reports current participation or receipt of benefits, respondents will be asked to report the total amount received over the past 12 months (in Philippine pesos), where applicable.
Programs covered include contributory social insurance schemes (e.g., GSIS, SSS), health insurance programs (PhilHealth—individually paid/employed and indigent program, and private health insurance or HMOs), private insurance companies, public employment programs (Cash-for-Work/Food-for-Work), conditional and unconditional cash transfer programs (including Pantawid Pamilyang Pilipino Program [4Ps], Walang Gutom, and other cash transfers), agricultural support programs such as the National Urban and Peri-Urban Agriculture Program (NUPAP), Social Pension, and Assistance to Individuals in Crisis Situations (AICS).
- **Income and other receipts:** Information on household income and other receipts will be collected for the period April 2025 to April 2026. Respondents will be asked whether they or any household member received income from various sources and, if so, the total amount received in Philippine pesos. Categories include cash assistance and remittances (from relatives abroad or domestically, friends, and others), pensions and retirement benefits, rental income (from land, housing, commercial space, or share of produce), interest and dividends (from bank deposits, loans, or investments), and other receipts such as proceeds from the sale of property, loans obtained, repayment of money lent, withdrawal of savings or business capital, gambling or lottery winnings, inheritance, prizes, and other miscellaneous sources.

3.6. Data collection households and individuals

- **Household survey:** household-level data will be collected using a structured and pretested questionnaire which. The household survey will begin with a roster of all household members to establish composition and basic demographic characteristics. The meal planner will subsequently respond to modules related to:
 - Nutrition knowledge
 - Household food consumption patterns over specified recall periods;
 - Food and non-food expenditures;
 - Household experiences related to food access;
 - Participation in social protection and assistance programs;
 - Income sources and other receipts during the reference period;
 - Engagement in gardening, foraging, and entrepreneurial activities.
 - Household assets

Where relevant, recall periods will follow those defined in the outcome descriptions (e.g., seven-day, four-week, six-month, or 12-month reference periods), and enumerators will use standardized probes to improve accuracy and completeness of responses.

- **Individual-Level Data Collection**

For women of reproductive age (WRA) and children under five years, we will conduct dietary intake assessment using 24-hour recall and anthropometric measurements.

- **24-hour dietary recall:** We will record food consumption for WRA and children under 5y through a quantitative 24-h recall administered by a trained surveyor. A second quantitative 24h recall will be conducted on 20% subsample, on 2 nonconsecutive weekdays within 1 or 2 weeks for the same mothers/children. The 24-h recall interview technique will be adapted from the multiple-pass method: 1) a list of meals, dishes, and all food items and beverages consumed will first be recorded and their place of preparation (at home or outside) will be noted; 2) interviewees will be asked for a full description of ingredients in all mixed dishes; 3) the method of preparation will be noted (e.g. time of cooking, whether the cooking receptacle is covered); 4) amounts (using household measures, direct weighing, or food models as appropriate) will be assessed separately for each ingredient and the portions eaten; 5) waste and non-consumed parts will be estimated; and 6) interviewees will systematically be prompted for specific foods of interest to the study, such as snacks and drinks. We will also collect data on where each food consumed was obtained. Catalogs of standard recipes will be created, one for dishes prepared and consumed at home and one for dishes consumed outside the home (data to be collected among restaurants and other food outlets, including street-food vendors). Finally, an algorithm will be developed to ensure that all days of the week are properly represented in the sample.
- **Anthropometric measurement:** Anthropometric data (height and weight) will be measured directly by trained field staff using standardized equipment and procedures. Measurements will follow internationally recognized protocols to ensure quality and comparability.

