3.4. Sample size

Sample size calculations account for the cluster design of the study and adjust for intra-cluster correlation. The analysis assumes a statistical power of 80% and a significance level (alpha) of 0.05. The study is powered to detect meaningful differences in key outcomes such as food security, hunger, dietary quality and nutrient intakes. This resulted in a sample size of 5320 households in total.

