3.5. Study outcomes

The study will collect data on a wide range of nutrition and health outcomes on household meal planner, WRA and their children <5y.

Primary outcomes

- **Nutrition knowledge:** Nutrition knowledge will be assessed through a structured questionnaire administered to the primary caregiver or food preparer in each household. The instrument includes multiple-choice, true/false, and scenario-based items measuring understanding of food groups and their nutritional functions, dietary diversity and balanced meal composition, key micronutrient sources (e.g., iron- and vitamin-rich foods), maternal and child feeding practices, and awareness of the structured voucher allocation rules. Items are aligned with the content of the standard and enhanced SBCC sessions to ensure relevance. A composite nutrition knowledge index will be constructed by summing correct responses and standardizing scores for analysis. Subdomain scores (e.g., dietary diversity knowledge, micronutrient knowledge, child feeding knowledge) will also be generated to assess which dimensions of knowledge were most responsive to the intervention.
- **Energy, macro- and micro-nutrient intake:** These outcomes will be assessed using data collected through 24h dietary recall. Using the dietary intake data, we will estimate the intake of energy, carbohydrate, protein, fat, and eleven micronutrients: vitamin A, thiamin, riboflavin, niacin, vitamin B-6, folate, vitamin B-12, vitamin C, calcium, iron, and zinc. Except for calcium, the probability of adequacy for each micronutrient and each individual in the sample will be calculated through the probability approach. Probabilities will be averaged across the 11 micronutrients to calculate the mean probability of adequacy, a summary indicator of diet quality.

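### The repeat 24-hour recalls are confined to weekdays, so the only within-person diet data may miss or underrepresent two of the seven days

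*Protocol*

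**What the plan says.** Everyone in the diet component gets one recall (Protocol, section 3.6, Data collection households and individuals, 24-hour dietary recall): "We will record food consumption for WRA and children under 5y through a quantitative 24-h recall administered by a trained surveyor". No day of the week is excluded for it.

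The repeat is limited in number and in days: "A second quantitative 24h recall will be conducted on 20% subsample", and this is to be done "on 2 nonconsecutive weekdays within 1 or 2 weeks for the same mothers/children".

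The same paragraph ends with a coverage rule: "an algorithm will be developed to ensure that all days of the week are properly represented in the sample".

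The recalls feed a primary outcome in section 3.5 (Energy, macro- and micro-nutrient intake). There a probability of adequacy is wanted for each person, and the summary is a mean over nutrients: "Probabilities will be averaged across the 11 micronutrients to calculate the mean probability of adequacy". The protocol does not say how the repeat recalls enter that calculation.

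**The concern.** A single 24-hour recall mixes a person's usual intake with day-to-day variation. To describe usual intake, or the probability that it is adequate, the day-to-day part has to be estimated and removed, and only repeated recalls on the same person can supply it. The 20% subsample is the only such repeat in the protocol.

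If those repeats fall only on Monday to Friday while first recalls cover all seven days, the variance being removed comes from a narrower set of days than the intakes it corrects. Where weekend intake differs on average, too little is removed and the usual-intake distribution stays too wide. Estimated levels of adequacy are then pulled towards 50%. Days never observed in the repeats cannot be recovered at the analysis stage.

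**Working it through.** **Inputs from the protocol.** One recall for all; repeats in 20%; repeats on two nonconsecutive weekdays; all days to be represented in the sample. The protocol gives no figure for weekend differences or variance components, so there is none of its own to reproduce here.

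**Assumptions.** Weekend days should be 2/7 of recalls. Weekend intake differs from weekday intake by d = 0.3 to 0.6 within-person SD, the full seven-day within-person variance being 1. Within-person variance W is twice between-person variance B. First recalls cover all seven days, and each recall covers the day before the interview.

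**Step 1: can both rules be met?** Yes.
- Both recalls of the 20% on weekdays, balance wanted in first recalls: weekend share needed in the other 80% = (2/7)/0.8 = 35.7%.
- The same, balance wanted in all recalls: (2/7) × 1.2/0.8 = 42.9%.
- Only the second recall on a weekday, balance in all recalls: (2/7) × 1.2 = 34.3% of first recalls.
- With no such compensation (subsample weekday-only, the rest spread evenly), weekend days are 0.8 × 2/7 = 22.9% of first recalls and 22.9%/1.2 = 19.0% of all recalls, against 28.6%.

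Oversampling weekends among the first recalls repairs the sample as a whole. It does nothing for the pairs.

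**Step 2: variance missed by the pairs.** Over seven days the weekend shift contributes (2/7)(5/7)d² = 0.204 d² to W.

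| Reading of the rule | Captured | Lost | W too small, d = 0.3 to 0.6 | B too large (twice that) |
|---|---|---|---|---|
| Both recalled days Monday-Friday | 0 | 0.204 d² | 1.8% to 7.3% | 3.7% to 14.7% |
| Both interview days Monday-Friday | (1/5)(4/5)d² = 0.160 d² | 0.044 d² | 0.4% to 1.6% | 0.8% to 3.2% |

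In the second row the recalled days are Sunday to Thursday. Friday and Saturday are missing, but Sunday is one of the five, so most of the weekend component is kept. The last column follows because the total B + W is taken from the first recalls: what is lost from W is added to B, and W = 2B doubles the relative error.

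If only the second recall is limited to recalled weekdays and the first may fall on any day, weekend days are half of 2/7, or 14.3%, of the recalls in the pairs. They are underrepresented but not absent.

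**Step 3: effect on a prevalence.** An excess of 3.7% to 14.7% in B makes the usual-intake SD √1.037 = 1.018 to √1.147 = 1.071 times too wide. With normal usual intake and a fixed cut-point, the error is largest about one SD from the mean, roughly 0.242 × ln(1.018) = 0.4 to 0.242 × ln(1.071) = 1.7 percentage points (0.242 is the standard normal density at 1). It is zero where prevalence is 50%.

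**The case against.** A reader might infer that the two scheduling rules contradict each other. They do not. The weekday limit belongs to the 20% subsample and the coverage rule to the whole sample, and Step 1 shows that both can be met. Weekdays may also be loose wording for days of the week, in which case nothing is lost and only the word needs changing. The text does not settle whether the two days are the first and second recall of a pair or two repeats, nor whether the interview day or the recalled day is meant. The larger figures hold only on the least favourable of these readings.

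A reader might also infer that the trial's comparisons are biased. The documents do not support that. The same rule applies in every arm, and the calculation concerns levels of adequacy. How the repeats enter the model, including any weekend adjustment, is ordinary content for an analysis plan that is not at hand.

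All of this stands, and it limits the size of the point. What remains is a scheduling rule that the protocol does state. Read in the ordinary sense, it leaves the within-person data short of weekend days, and no analysis plan can add days that were not observed.

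A third tempting inference is that calcium has no probability of adequacy, so that the mean cannot exceed 10/11 = 0.909 and arm differences shrink by 9.1%. Section 3.5 says: "Except for calcium, the probability of adequacy for each micronutrient and each individual in the sample will be calculated through the probability approach". The exception qualifies the method, and the average over 11 that follows implies that calcium has a value by a rule not named. The 0.909 ceiling would apply only if calcium were scored zero, which the average over 11 argues against.

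**Conclusion.** The point holds as a tension in the recall schedule, not as a contradiction. Read as Monday to Friday, the rule makes the repeat pairs miss or underrepresent two of the seven days. Within-person variance taken from them would be about 2-7% too small if both recalled days are weekdays, or about 0.4-1.6% if both interview days are. Between-person variance would be about 4-15% or 0.8-3.2% too large. These ranges rest on the assumed weekend shift and 2:1 variance ratio, and on the repeats being used to derive usual intake or adequacy, which the protocol implies without saying. The consequence is a modest error in levels of adequacy. No bias in arm contrasts is shown. It is worth correcting because the change is cheap and must come before fieldwork.

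Calcium is a matter for clarification only. The list "eleven micronutrients: vitamin A, thiamin, riboflavin, niacin, vitamin B-6, folate, vitamin B-12, vitamin C, calcium, iron, and zinc" does count to 11, but a method is named for 10. With m the mean of those 10 and c the calcium value, the index is (10m + c)/11, which differs from m by (c − m)/11. For assumed m of 0.3 to 0.7 and c of 0 to 1, that is −0.064 to +0.064.

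**What to change.** In section 3.6, replace weekdays with days of the week in the sentence on the repeat recall. Say that first and repeat recalls are scheduled by the same seven-day algorithm, on nonconsecutive days with weekends included. State whether the algorithm refers to the recalled day or the interview day, and whether the two days are the first and second recall or two repeats. The cost is a line of protocol text and some weekend interviews in a fifth of the diet sample.

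As a minor clarification in section 3.5, either state the rule for calcium and keep 11 nutrients, or average over 10. This costs one sentence.
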